#### **4.2.2 Contents of Label**

The information written on the label includes specification that the drug is for use in a clinical trial, the code name, lot number, expiration date, and storage conditions of the IMP, and the name and address of the sponsor.

## **5 Trial Population**

### **5.1 Target Disease**

AML

### **5.2 Inclusion Criteria**

Patients meeting all of the following criteria at the time of screening will be included in this trial:

- 1) Male or female patients with a diagnosis of AML (World Health Organization [WHO] classification 2008).
  - Patients, 20 years of age or older, who are unresponsive to standard chemotherapy or have relapsed following standard chemotherapy
  - Patients, 65 years of age or older, who are not eligible for standard intensive chemotherapy and who meet at least one of the following criteria (applicable to Cohorts 1, 2, and 4 only):
    - AML from MDS, or secondary AML

- Chromosomal karyotype abnormality with poor prognosis [del (5q), del (7q), -5, -7, abnormality of 3q (q21;q26), t (6;9) (p23;q34), t (9;22) (q34;q11.2), abnormality of 11 (11q23), or complex karyotype of 3 or more unrelated abnormalities of any kind]
  - Dysfunction of the heart (left ventricular ejection fraction [LVEF] < 50%) or lung (diffusing capacity of the lung for carbon monoxide [DLCO] or forced expiratory volume in the first second [FEV 1] < 50% of expected value) which is unrelated to AML
  - ECOG PS of 2
  - 75 years of age or older
- 2) Patients with ECOG PS of 0 to 2.
  - 3) Patients with adequate vital organ function (patients whose clinical laboratory values meet the following conditions).
    - a) Hepatic function: total bilirubin (T-Bil)  $\leq 2 \times$  upper limit of normal (ULN); AST and ALT  $\leq 2.5 \times$  ULN.
    - b) Renal function: serum Cr  $\leq 1.5 \times$  ULN.
  - 4) Female patients of childbearing potential must not be pregnant or breast feeding (pregnancy test will be performed at screening). Female patients of childbearing potential and all male patients must practice two medically acceptable methods of birth control and must not become pregnant or father a child while receiving treatment with SGI-110 and for 3 months following last dosing. If male patients have female partners of childbearing potential, those partners must also practice medically acceptable methods of birth control for the same period.
  - 5) Patients who have undergone prior allogeneic hematopoietic stem cell transplantation must have no evidence of active graft-versus host disease (GVHD) and must be off immunosuppressive therapy by  $\geq 2$  weeks prior to the scheduled start of IMP administration.
  - 6) Patients who have undergone no major surgery within 4 weeks prior to the scheduled start of IMP administration.
  - 7) Patients who have undergone no chemotherapy within 2 weeks prior to the scheduled start of IMP administration, nor hematopoietic stem cell transplantation within 8 weeks prior to the scheduled start of IMP administration.
  - 8) Patients who are able to provide written consent to participate in this trial by signing an informed consent form (ICF) that has been approved by an Institutional Review Board (IRB) (patients who are willing to comply with the protocol, including consent to hospitalization during Course 1).

[Rationale for inclusion criteria]

1) The target population of the trial will be patients with AML who are expected to respond to SGI-110 in reference to a preceding clinical trial conducted outside of Japan (Study SGI-110-01). It has been decided to select patients who do not respond

to conventional therapy or for whom generally accepted standard therapy are not available in accordance with the “Guidelines for Clinical Evaluation of Antimalignant Tumor Drugs.” The lower limit of age is set as 20 years for patients who are unresponsive to standard therapy or have relapsed after treatment since informed consent can be obtained from subjects aged 20 years or older. The lower limit of age is set as 65 years for patients who are not eligible for standard intensive chemotherapy in reference to studies conducted outside of Japan.

As mentioned in [Section 1.2.3](#) Trial Rationale, a regimen of SGI-110 at 60 mg/m^2 once daily for 10 days is planned to be adopted in Study SGI-110-06 in patients with relapsed or refractory AML. Therefore, the tolerability of SGI-110 at 60 mg/m^2 once daily for 10 days will be evaluated in patients with relapsed or refractory AML in Cohort 3 (60 mg/m^2 in 10-day regimen), which is consistent with the target population in Study SGI-110-06.

2), 3) These criteria have been provided to ensure the subjects’ safety in reference to the “Guidelines for Clinical Evaluation of Antimalignant Tumor Drugs.”

4) The criterion has been provided in consideration of the safety of fetuses and infants because SGI-110 has shown genotoxicity, teratogenicity, fetotoxicity, and embryotoxicity and it is unknown whether or not SGI-110 is transferred into breast milk.

5) to 7) The criteria have been provided to select patients having no effect of previous treatment in reference to the “Guidelines for Clinical Evaluation of Antimalignant Tumor Drugs” and a study conducted outside of Japan (Study SGI-110-01).

8) The criterion has been provided for ethical reasons based on Good Clinical Practice. Hospitalization during Course 1, which is the DLT evaluation period, is to be mandatory in reference to the “Guidelines for Clinical Evaluation of Antimalignant Tumor Drugs.”

### 5.3 Exclusion Criteria

Patients falling under any of the following criteria at the time of screening will be excluded from this trial:

- 1) Patients with acute promyelocytic leukemia (APL) accompanied by t(15;17)(q22;q12) or (PML/RARA) karyotype abnormalities (including other variant types of APL).

- 2) Patients with multiple cancers (except for adequately treated basal cell or squamous cell skin cancer, in situ cervical cancer, or other cancer from which the subject has been disease free for at least 3 years).
- 3) Patients with life-threatening illnesses other than AML, such as uncontrolled medical conditions or organ system dysfunction which, in the opinion of the investigator or subinvestigator, could compromise the subject's safety or the study outcomes.
- 4) Patients with poorly controlled arrhythmias, or any Class 3 or 4 cardiac disease as defined by the New York Heart Association (NYHA) Functional Classification.
- 5) Patients with symptomatic central nervous system involvement.
- 6) Patients who have received radiation therapy for extramedullary disease within 2 weeks prior to planned enrollment.
- 7) Patients with AEs (other than alopecia) of Grade 2 or higher from prior therapy for AML, at the time of screening for this trial.
- 8) Patients with febrile neutropenia.
- 9) Patients who are human immunodeficiency virus (HIV) antibody positive, hepatitis B virus (HBV)-DNA positive, or with active hepatitis C.
- 10) Patients who have taken any investigational drug or individually imported drug within 2 weeks prior to the scheduled start of IMP administration.
- 11) Patients who have been treated with systemic corticosteroids as treatment for their AML within 2 weeks prior to the scheduled start of IMP administration.
- 12) Patients with uncontrolled active systemic infections.
- 13) Patients who have hypersensitivity to decitabine, SGI-110, or IMP excipients.
- 14) Patients judged to be ineligible by the investigator or subinvestigator for any other reason.

[Rationale for exclusion criteria]

1) Patients with APL will be excluded because it is reported that the remission rate is high in patients treated with all-trans retinoic acid, arsenic trioxide, etc.

2), 5), 6), 10), 11) These criteria have been provided for reasons of subject safety and because the conditions mentioned in these criteria may affect efficacy evaluation.

3), 4), 7) to 9), 12), 13) These criteria have been provided for reasons of subject safety.

14) The criterion has been provided so that the investigator or subinvestigator can consider factors other than those mentioned above when selecting subjects.

Reference: NYHA Functional Classification

I	Presence of heart disease, but no limitation of physical activity. Ordinary physical activity does not cause undue fatigue, palpitation, dyspnea (shortness of breath), or anginal pain.
II	Slight limitation of physical activity. Comfortable at rest.

	Ordinary physical activity results in fatigue, palpitation, dyspnea (shortness of breath), or anginal pain.
III	Marked limitation of physical activity. Comfortable at rest. Less than ordinary activity causes fatigue, palpitation, dyspnea, or anginal pain.
IV	Unable to carry on any physical activity without discomfort because of heart disease. Symptoms of heart failure or anginal pain at rest. If any physical activity is undertaken, discomfort increases.
(Additional)	IIs: Slight limitation of physical activity IIIm: Moderate limitation of physical activity

Source: Guidelines for Diagnosis and Treatment of Cardiovascular Diseases (2004-2005 Joint Working Group report)

Guidelines for Treatment of Acute Heart Failure (2006 revision) - Digest Version

Societies participating in the Joint Working Group: Japanese Circulation Society, Japanese Association for Thoracic Surgery, Japanese Society for Cardiovascular Surgery, Japanese College of Cardiology, and Japanese Heart Failure Society

[http://www.j-circ.or.jp/guideline/pdf/JCS2006\\_maruyama\\_d.pdf](http://www.j-circ.or.jp/guideline/pdf/JCS2006_maruyama_d.pdf)

## 6 Trial Design

### 6.1 Dose, Regimen, and Treatment Period

The total daily dose will be determined based on the subject's body surface area (BSA) calculated from height and weight prior to administration in each course, according to the treatment cohort.

SGI-110 will be administered SC at the determined daily dose after being reconstituted using the custom diluent provided.

In Cohorts 1, 2, and 4, subjects will receive SGI-110 once daily for 5 consecutive days (Day 1 to Day 5), followed by a 23-day non-dosing period (Day 6 to Day 28). One course will consist of 4 weeks (28 days). In Cohort 3, subjects will receive SGI-110 once daily for 10 days in total (SGI-110 will be administered for 5 consecutive days [Day 1 to Day 5], suspended for 2 days [Day 6 and Day 7], then administered for another 5 consecutive days [Day 8 to Day 12]), and the dosing will be suspended for 16 days (Day 13 to Day 28). One course will consist of 4 weeks (28 days).

The dose and regimen for each cohort is as follows:

Cohort 1 ( $36 \text{ mg/m}^2$ , 5-day administration)

Cohort 2 ( $60 \text{ mg/m}^2$ , 5-day administration)

Cohort 3 ( $60 \text{ mg/m}^2$ , 10-day administration [ie, 5-day administration twice, with a non-dosing period in-between])

Cohort 4 ( $90 \text{ mg/m}^2$ , 5-day administration)

SGI-110 for injection, 100 mg contains SGI-110 equivalent to 100 mg of free acid, as a lyophilized powder in a 5-mL glass vial. Subjects who complete IMP administration and all observations during the DLT evaluation period, and who do not have any apparent progression of AML, will be permitted to continue treatment with IMP following the DLT evaluation period if they wish, and will receive treatment according to the same dosing schedule as Course 1 (Cohorts 1, 2, and 4).

In Cohort 3, subjects will receive SGI-110 for 10 days in Course 1 (DLT evaluation period), for 10 or 5 days in Course 2 (Extended treatment period), for 5 days in Course 3 and subsequent courses. The investigator will determine whether or not the transition to Course 2 should be postponed and which regimen is used for each subject, as described below, based on the subject's condition (the percentage of blasts in the peripheral blood and bone marrow, and peripheral blood cell counts) at the completion of Course 1.

- 1) Has blasts in the peripheral blood: Subject will proceed to Course 2 without delay and receive SGI-110 for 10 days.
- 2) No blasts in the peripheral blood: The percentage of blasts in the bone marrow will be assessed.
  - a) The percentage of blasts in the bone marrow is  $\geq 5\%$ : Subject will proceed to Course 2 without delay and receive SGI-110 for 10 days.
  - b) The percentage of blasts in the bone marrow is  $< 5\%$ : The neutrophil and platelet counts in the peripheral blood will be assessed.
    - i) The neutrophil count is  $\geq 500/\mu\text{L}$  and platelet count is  $\geq 50000/\mu\text{L}$ : Subject will proceed to Course 2 without delay and receive SGI-110 for 5 days.
    - ii) The neutrophil count is  $< 500/\mu\text{L}$  or platelet count is  $< 50000/\mu\text{L}$ : Transition to Course 2 will be postponed, and the subject's peripheral blood will be assessed at least once a week. After that, if the subject has no blasts in the peripheral blood but the neutrophil and platelet counts are recovered to  $\geq 500/\mu\text{L}$  and  $\geq 50000/\mu\text{L}$ , respectively, he/she will proceed to Course 2 and receive SGI-110 for 5 days. If blasts are found in the subject's peripheral blood while his/her transition to Course 2 is on hold, he/she will proceed to Course 2 and receive SGI-110 for 10 days. For subjects whose transition to Course 2 is on hold because blasts are not found in his/her peripheral blood and the neutrophil and platelet counts are  $< 500/\mu\text{L}$  and  $< 50000/\mu\text{L}$ , respectively, it is possible to proceed to Course 2 and receive SGI-110 for either 5 or 10 days at the discretion of the investigator or subinvestigator based on the benefit-risk balance for the subject.

SGI-110 diluent for reconstitution, 3 mL contains 3 mL of custom diluent for reconstitution in a 5-mL glass vial.

SGI-110 for injection, 100 mg vial and SGI-110 diluent for reconstitution, 3 mL should be stored at 2°C to 8°C and 2°C to 30°C, respectively, until use. Both vials are for single use only as they are free of preservatives.

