### **3 Trial Plan**

#### **3.1 Trial Design**

This is a phase 1, multicenter, open-label study to evaluate the tolerability of SGI-110 in Japanese patients with relapsed or refractory AML after undergoing standard therapy or Japanese patients with AML aged 65 years or older who are not eligible for standard chemotherapy.

This trial consists of a screening period, DLT evaluation period, and withdrawal examination. Subjects who complete IMP administration and all observations during the DLT evaluation period, and who do not have any apparent progression of AML, will be permitted to continue treatment with IMP following the DLT evaluation period if they wish. The primary evaluation data for Cohorts 1, 2, and 4 will have a cutoff date of 31 May 2016 and the data for Cohort 3 will have a cutoff date of 30 Nov 2017. The period up until the data cutoff will be defined as the primary evaluation part. This will be followed by an extended treatment part to assess long-term safety, which will include those subjects on IMP treatment who have consented to participate in the extended treatment part. Transition from the primary evaluation part to the extended treatment part will take place at the start of the next course after the data cutoff.

Administration of the IMP will be started in Cohort 1 (36 mg/m^2 in 5-day regimen) and 3 subjects will receive the IMP in this cohort. If none of the 3 subjects has a DLT during the DLT evaluation period, the study will proceed to the next cohort. If one of the 3 subjects experiences a DLT, 3 additional subjects will be enrolled and DLTs will be evaluated in a total of 6 subjects. The study will proceed to the next cohort only if no more than one of the 6 subjects has a DLT. If the number of subjects exhibiting a DLT within a cohort is  $\geq 2/3$  or  $\geq 2/6$ , there will be no dose escalation.

In Cohort 2 (60 mg/m^2 in 5-day regimen) and Cohort 4 (90 mg/m^2 in 5-day regimen), DLTs will be assessed in the same manner. However, even if none of the first 3 subjects enrolled has a DLT, a total of 6 subjects will be enrolled in each of Cohorts 2 and 3 of which the dose has been determined as the recommended dose for a next phase study.

Based on the occurrence of DLTs, the tolerability at the recommended dose for a next phase study will be confirmed in Japanese subjects as well.

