### 3.5 Rules to Be Observed for Enrollment and Treatment

- 1) The dose or regimen should remain unchanged for each subject, and no subject should be re-enrolled.
- 2) In order to avoid occurrence of unexpected serious adverse drug reactions in multiple subjects, the IMP should be administered to the second subject after the following day of Day 1 of Course 1 in the first subject at each dose level.
- 3) When the administration or examination scheduled for Course 1 cannot be implemented for reasons other than safety, the subject should be excluded from the DLT evaluation, and another subject should be enrolled.
- 4) Administration of SGI-110 is expected to cause myelosuppression and infection (eg, febrile neutropenia, pneumonia, and sepsis). Delay or discontinuation of administration should be determined for subjects who have experienced or are suspected to have experienced pyrexia or infection based on data from laboratory tests, physical examination (body temperature), and imaging tests before the start of the next course and continuing the treatment.
- 5) In and after Course 2 (extended treatment period), IMP administration may be suspended (skipped) from Day 2 and onwards at the discretion of the investigator or subinvestigator, depending on the subject's condition. Subjects who fall under any of the discontinuation criteria should be withdrawn from the trial.

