## 7.2.3 Efficacy Evaluation

### 7.2.3.1 Assessment Based on Response Criteria

The investigator or subinvestigator will evaluate response in each course in accordance with the response criteria in [Table 7.2-1](#), which is based on the response criteria for AML treatment established by an international working group, and will document evaluation results in the medical records and CRF. The evaluation results to be documented in the medical records and CRF will be “not evaluable (NE)” when no bone marrow examination has been performed, “progressive disease” when disease clearly progressed without CR, CRi, or CRp achieved after the start of IMP administration, or “no response” when no remission or relapse has been confirmed in the course.

The best overall response for each subject and the date of the first response (CR, CRi, or CRp) will be documented in the medical records and CRF at the time of trial completion or withdrawal from the trial. Also recorded will be the date of the first relapse, if relapse occurred thereafter, and the date of the last evaluation, if no relapse occurred.

Table 7.2-1 Response Criteria		
	Bone Marrow	Peripheral Blood
CR	
 
Blast cells < 5%
 
	
 
Neutrophil count > 1,000/<math>\mu</math>L
 
Platelet count <math>\geq</math> 100,000/<math>\mu</math>L
 
No blast cell
 
Transfusion independence
 

CRp	
 
Blast cells < 5%
 
	
 
Neutrophil count > 1,000/<math>\mu</math>L
 
Platelet count < 100,000/<math>\mu</math>L
 
No blast cell
 
RBC transfusion independence
 

Morphologic CRi	
 
Blast cells < 5 %
 
	
 
Neutrophil count < 1,000/<math>\mu</math>L
 
No blast cell
 

PR	
 
Rate of decrease in blast cells in the bone marrow <math>\geq</math> 50% and ratio of blast cells of 5% to 25%
 
	
 
Neutrophil count > 1,000/<math>\mu</math>L
 
Platelet count <math>\geq</math> 100,000/<math>\mu</math>L
 
No blast cell
 

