Relapse	
 
Leukemia cells (blast cells) <math>\geq</math> 5% in the bone marrow or presence of leukemia cells (blast cells) in the peripheral blood are manifested again after CR, CRi, or CRp has been achieved.
 
Leukemia cells with abnormal chromosomes are revealed again in chromosomal testing.
 
	

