### **9.2 Criteria and Procedures for Withdrawal of Individual Subjects**

In any of the events listed below, the investigator or subinvestigator will withdraw the subject from the trial, perform the tests such as the withdrawal examination stipulated in [Section 7.1](#) Schedule and Procedures, and promptly inform the sponsor of the withdrawal (Annex 1 Emergency Contact). The investigator or subinvestigator will record the date and reason for withdrawal in the CRF.

For subjects who do not undergo the withdrawal examination, the date of withdrawal will be the day when the investigator or subinvestigator deems withdrawal is necessary.

If withdrawal is necessitated by problems with safety, such as the occurrence of an AE or aggravation of the underlying disease, the investigator or subinvestigator will promptly take appropriate measures and perform follow-up if necessary (refer to [Section 8.4](#) Follow-up Investigation of Adverse Events).

- 1) Apparent progression (including the relapse) of the primary disease.
- 2) Dose-limiting toxicity that does not improve to the baseline level or show improvement by at least 1 grade within 4 weeks, or occurrence of another DLT.
- 3) Delay in commencement of the next course by more than 4 weeks due to an AE, unless the investigator or subinvestigator judges that continuation of SGI-110

administration is in the patient's best interest, in which case the delay may be extended by another 2 weeks.

- 4) Subject becomes pregnant.
- 5) Subject wishes to withdraw from the trial.
- 6) The investigator or subinvestigator judges that it is difficult to continue IMP administration due to occurrence of an AE.
- 7) The investigator or subinvestigator judges that it is necessary to discontinue IMP administration for any other reason.

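### Cohort 3: when blood blasts return in a subject held in CRi or CRp, Protocol 6.1 requires a 10-day Course 2 and 9.2 requires withdrawal, with no stated precedence

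*Protocol*

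**What the plan says.** **The hold.** Protocol 6.1 2) b) ii) applies to a Cohort 3 subject at the end of Course 1 with no blasts in the blood, marrow blasts below 5%, and neutrophils below 500/µL or platelets below 50,000/µL. For this subject, "Transition to Course 2 will be postponed, and the subject's peripheral blood will be assessed at least once a week". If blasts are then found in the blood "while his/her transition to Course 2 is on hold, he/she will proceed to Course 2 and receive SGI-110 for 10 days".

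**Response and relapse.** Table 7.2-1 (Protocol 7.2.3.1, repeated in SAP 6.2.5) has a category "Morphologic CRi": marrow blasts below 5%, no blood blasts, neutrophils below 1,000/µL. CRp needs neutrophils above 1,000/µL, platelets below 100,000/µL and independence from red cell transfusion. The relapse row covers leukemia cells that "in the peripheral blood are manifested again after CR, CRi, or CRp has been achieved". It sets no minimum blood count and no confirmation step.

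**Withdrawal.** Protocol 9.2 opens: "In any of the events listed below, the investigator or subinvestigator will withdraw the subject from the trial". Its first criterion, repeated in the synopsis, is "Apparent progression (including the relapse) of the primary disease". Section 3.5 item 5 adds: "Subjects who fall under any of the discontinuation criteria should be withdrawn from the trial". Section 3.1 limits continuation after the DLT evaluation period to subjects "who do not have any apparent progression of AML, will be permitted to continue treatment with IMP".

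**The concern.** For a subject who reached remission before or at the hold, the finding that triggers the 10-day Course 2 in 6.1 is also the finding that triggers withdrawal in 9.2. An investigator cannot obey both, and two investigators could act differently on identical patients while each follows the protocol.

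This is a treat-or-stop decision in the only cohort that studies the 10-day regimen. It determines whether the subject counts as exposed in Course 2 or as discontinued, and for what reason. It also touches the DLT period. Under 3.1 and 7.1, a subject whose Course 2 is postponed stays in that period until Course 2 dosing starts. If the subject is withdrawn instead, Course 2 never starts and the text gives no other end for the period.

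**Working it through.** The plan gives no figure to reproduce, so the check is one of logic: classify each way of entering the hold by Table 7.2-1, then apply the relapse row and 9.2.

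**Step 1. Response status of held subjects.** All have marrow blasts below 5% and no blood blasts. A marrow result must exist, because branch 2) b) cannot be reached without one and marrow aspiration is scheduled for Day 29 of Course 1.

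| Neutrophils (/µL) | Platelets (/µL) | Red cell transfusion | Held? | Table 7.2-1 |
|---|---|---|---|---|
| <500 | any | any | yes | CRi |
| 500–999 | <50,000 | any | yes | CRi |
| >1,000 | <50,000 | independent | yes | CRp |
| >1,000 | <50,000 | dependent | yes | none |
| exactly 1,000 | <50,000 | any | yes | none |

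Every neutrophil-triggered hold is CRi, because the hold threshold of 500 lies below the CRi threshold of 1,000. A platelet-only hold is CRi or CRp except in the last two rows.

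**Step 2. Blasts appear in the blood during the hold.** In the first three rows the subject has achieved CRi or CRp, so the relapse row is met. In the last two rows it is not met on this basis, and 6.1 raises no conflict with the relapse criterion.

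**Step 3. Required action in the first three rows.**

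| Source | Action |
|---|---|
| 6.1 2) b) ii) | proceed to Course 2, 10-day regimen |
| 9.2 criterion 1; synopsis | withdraw |
| 3.1 | continuation only without apparent progression |
| 3.5 item 5 | withdraw if any discontinuation criterion is met |

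Item 5 of 3.5 begins with Course 2 and later, so its reach to a subject still awaiting Course 2 is arguable. Section 9.2 has no such limit.

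**Step 4. Search for precedence.** Neither 6.1 nor 9.2 refers to the other on this point. Where 9.2 allows an exception it writes it into the criterion: criterion 3, on delay from an adverse event, lets the investigator extend the delay. Criterion 1 has no exception.

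**Step 5. Size.**
- Planned exposure: 10 doses × 60 mg/m² = 600 mg/m² under 6.1; 0 under 9.2.
- Weight of one subject in Cohort 3: 1/6 = 16.7 percentage points in any rate with all 6 in the denominator.
- Frequency: being held, in CRi or CRp, and then relapsing. The documents give no rate for this sequence.

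**The case against.** The best defence is that the specific rule governs the general one. Section 6.1 2) b) ii) was written for exactly this event, while 9.2 is a trial-wide list that speaks of *apparent* progression, which may leave room for judgement over a few blasts. Other branches of 6.1 also give 10 days of drug when blasts are present. Applying 9.2 literally would leave the hold sentence with effect only in the last two rows of the Step 1 table.

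These are plausible readings of intent, but none is stated. Criterion 1 names relapse expressly, and the relapse row allows no discretion. The other branches cover subjects with blasts at the end of Course 1, who need not have reached remission; a held subject in CRi or CRp has.

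The defence is right that the reach is limited. A reader might infer more than the documents support:

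- **That safety data stop at withdrawal.** They do not. There is a withdrawal examination within 5 days (7.1.5). Unresolved events are generally followed up, and those possibly related continue until resolved or stable (8.4). Possibly related serious events remain reportable (8.2.2).
- **That remission duration is biased.** 7.2.3.1 already requires the first relapse date, and SAP 6.2.6 ends the duration at relapse, whether or not treatment continues. Bias would need sites to leave relapses unrecorded, which nothing in the documents suggests.
- **That the 16% composite remission rate (8 of 50) in 1.2.2.1.1.2 shows how often the conflict arises.** It comes from 5-day dosing at 60 and 90 mg/m²; that section reports no efficacy data for 10 days. It counts any composite remission, not a hold followed by relapse.
- **That nearly every held subject is in remission.** A platelet-only hold with neutrophils above 1,000/µL and red cell transfusion dependence is not, and 6.2.2 expects transfusion as supportive care. The share is not given.

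**Conclusion.** The inconsistency is real. For a Cohort 3 subject held in CRi or CRp, one event carries two mandatory and opposite instructions, 10 planned doses or withdrawal, with no order of precedence. It affects Course 2 exposure, the number of and reasons for discontinuations, and the end of the DLT period for a postponed subject.

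The conclusion rests on reading Table 7.2-1 as written and on the absence of any exempting text in the protocol or SAP. That sites would actually diverge is an inference from the two instructions.

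It should be corrected, but it does not undermine the trial. The conflict is conditional on a hold followed by relapse, at an unknown frequency. The primary endpoint is DLT in Course 1, Cohort 3 sets no MTD for the 10-day regimen, and SAP 6.5 plans no tests or interval estimates. The DLT criteria themselves are unaffected; what is left open is where a held and then withdrawn subject's DLT period ends.

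**What to change.** Reconcile 6.1 2) b) ii) with 9.2 criterion 1, the synopsis discontinuation criteria, 3.5 item 5 and 3.1, so that blasts returning in the blood during a hold lead to one stated action. A cross-reference or an explicit exception, placed in both 6.1 and 9.2, is enough. Which action applies is the sponsor's clinical decision and is not judged here.

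In the same amendment, state in 3.1 and 7.1, and in the matching text of SAP section 3, when the DLT period ends for a postponed subject who never starts Course 2.

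A sentence in 7.2.3.1 and SAP 6.2.6 confirming that the relapse date ends remission duration even if treatment continues would only clarify what is already defined there, and is optional.

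The cost is a few sentences of protocol text, with a matching SAP edit. No new data, visits or analyses are needed.
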